### 7.2.1. Eligibility Criteria

### 7.2.2. Inclusion Criteria

#### *HCP KAB Survey*

To be eligible for participation in the study, HCPs must:

- Be a physician, nurse or pharmacist;
- Be able to independently complete the survey in English or French; and
- Meet one of the following criteria outside of a clinical trial setting:
  - Have prescribed CAB-LA for HIV PrEP in Canada; or
  - Have administered CAB-LA for HIV PrEP in Canada; or
  - Have been or are currently involved in some aspect of CAB-LA management for HIV PrEP in Canada.

#### *User KAB Survey*

To be eligible for participation in the study, individuals must meet all the following criteria:

- Provide a signed and dated informed consent form for participation in this research study;
  - Be capable of providing informed consent;
- Be at least 16 years of age at the time of consent into the study;
- Must be able to independently complete the survey in English or French; and
  - Have received at least one injection of CAB-LA for HIV PrEP.

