#### *User KAB Survey*

Individuals meeting any of the following criteria will be excluded from the study:

- Participation in a clinical study that may interfere with participation in this study (i.e., clinical studies assessing the efficacy of long acting injectables for PrEP), during the study period.

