## **7.3. Variables**

### **7.3.1. Exposure Definitions**

#### *HCP Survey*

For HCPs, exposure will be defined as having prescribed or managed use of CAB-LA for the prevention of HIV-1 among individuals at high risk in Canada eligible for CAB-LA based on the HC indication.

*User Survey*

For CAB-LA users, exposure will be defined as having previously initiated CAB-LA for the prevention of HIV-1. In the survey, this is defined as having received at least one dose of CAB-LA at the time of survey enrolment.

*Apretude Supports Program Database Analysis*

For CAB-LA users, exposure will be defined as having initiated CAB-LA for the prevention of HIV-1. In the Apretude Supports Program database analysis, this is defined as enrollment and initiation of CAB-LA through the Apretude Supports Program within the ascertainment period (i.e., have received at least one injection of CAB-LA, with the first dose taking place between July 2024 and October 2026). Data will be included for users until the end of the follow-up period (October 2027) or until discontinuation.

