### Recruitment of CAB-LA Users

For the survey component of the study, CAB-LA users will be recruited using recruitment flyers/posters with a quick response (QR) code linked to the survey, displayed at different clinical settings where they access PrEP (for example, but not limited to hospitals, outpatient clinics, and pharmacies) across Canada. In addition, HCPs participating in the HCP survey may also direct CAB-LA users to the QR code for the survey. To reach target sample sizes and to ensure representativeness of the user sample, recruitment may additionally be conducted through Mediscys. Recruitment of CAB-LA users will be conducted in geographic regions where CAB-LA is publicly listed. As access expands across Canada, recruitment will also be expanded to ensure representation from all possible regions. The data will be analyzed by geographical location, with some regions anticipated to be grouped together based on available sample size (e.g., Western Canada). Recruitment and survey materials for the secondary objectives will not contain language suggesting that the study was requested by HC.

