### Logistics and Monitoring

Individuals who are interested in participating will be directed to a brief screening questionnaire to assess eligibility for survey participation against study inclusion criteria. If the individual is identified as eligible to participate in the survey based on screener responses, they will be directed to an electronic version of the consent form. Once they have electronically indicated their consent to participate (selecting a consent statement and providing an electronic signature), they will subsequently be directed to complete the survey. Based on personal information collected during the screening and consent process, including participant name and email address, a check will be performed to ensure that there is no prior completion of the same survey in the system using the same name and email entered. The purpose of this check is to prevent participants from completing the same survey multiple times. To help optimize response rates, up to two reminder emails will be sent to individuals who have not completed the survey (one after 7 days and another after 14 days). To promote further education, correct responses to the survey questions, where applicable, will be displayed immediately after submission of the survey (before a participant has exited the survey) in a PDF file. A link to the aRMMs will be included in the PDF and on the online survey platform for future reference.

For each survey, a live dashboard will be set up to monitor recruitment progress against targets, allowing for adjustments to the recruitment strategy to be made in real time, as needed (e.g., increase the number of recruitment sites and/or target recruitment of certain participant groups to improve representativeness).

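### The user survey criterion does not exclude people whose only CAB-LA injections were given outside Canada or in an earlier trial, although the HCP criteria do and the primary aim concerns the aRMMs in Canada

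*Protocol*

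**What the plan says.** For HCPs, Section 7.2.2 sets the condition "Meet one of the following criteria outside of a clinical trial setting", and each of the three alternatives beneath it is tied to Canada, the first being "Have prescribed CAB-LA for HIV PrEP in Canada; or".

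For users, the only exposure condition in the same section is "Have received at least one injection of CAB-LA for HIV PrEP". It names no country, setting or date. The user exposure definition in Section 7.3.1 is equally open: "In the survey, this is defined as having received at least one dose of CAB-LA at the time of survey enrolment".

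The only trial-related restriction on users is the exclusion in Section 7.2.3, "Participation in a clinical study that may interfere with participation in this study". It gives efficacy studies of long-acting injectable PrEP as the case meant, and it applies during the study period.

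On recruitment, Section 7.5.2 places QR-code posters "displayed at different clinical settings where they access PrEP (for example, but not limited to hospitals, outpatient clinics, and pharmacies) across Canada". It adds that "Recruitment of CAB-LA users will be conducted in geographic regions where CAB-LA is publicly listed", that participating HCPs may refer users, and that a vendor may be used. Eligibility is decided by a "brief screening questionnaire to assess eligibility for survey participation against study inclusion criteria".

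**The concern.** Section 6.1 states the primary aim as evaluating how well the aRMMs work in Canada, at Health Canada's request. The intended user population is therefore people treated with CAB-LA in Canadian routine care, whom the education program is meant to reach. The user criterion is wider than that. It also admits a person now attending a Canadian PrEP clinic whose only injections were given in another country or in a trial that has ended.

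Such a person's access to the User Guide or Reminder Card, and their knowledge and behaviour scores, say little about the Canadian program. They would still count in the percentage compared with the 70% population cut-off in Section 7.3.2. Because Section 7.5.2 closes the survey at 250 users, each such respondent may also take the place of an intended one. If nobody asks where and how the injections were given, these respondents cannot reliably be identified afterwards.

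**Working it through.** **Step 1. The criteria side by side.**

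| Component | In Canada? | Outside a trial? | Source |
|---|---|---|---|
| HCP survey | Required | Required | Section 7.2.2 |
| User survey | Not stated | Only a concurrent interfering study is barred | Sections 7.2.2, 7.2.3, 7.3.1 |
| Program database | First injection July 2024 to October 2026; initiation outside the Canadian program excluded | Follows from the program data source | Sections 7.2.2, 7.2.3 |

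Only the user survey lacks an eligibility condition tying exposure to Canadian post-launch use.

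**Step 2. Does another provision close the gap?**

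- *Exclusion criterion.* It looks at the study period. Section 5.1 shows that CAB-LA was given in trials before the May 2024 approval, so completed trial use is possible and is not barred.
- *Recruitment setting.* It governs who is likely to see the poster. It is not an eligibility rule.
- *Screener.* As described, it tests the inclusion criteria, so it inherits their wording.
- *Province or territory of residence (Table 3).* It is collected as a descriptor. It is not an entry condition and does not show where injections were given.

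None of these makes such a person ineligible.

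**Step 3. The plan's own precision figure.** Table 13 uses 1.96 × √(p(1−p)/n). For n = 250:

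- p = 0.50: 1.96 × √(0.25/250) = 6.2 points
- p = 0.70: 1.96 × √(0.21/250) = 5.7 points

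Both match the table. The point here does not dispute them.

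**Step 4. How far could the result move?** Observed rate = (1 − f)·p + f·q, where f is the share of respondents treated only abroad or only in an earlier trial, p the pass rate among intended users, and q the pass rate in that share. None of the three is in the protocol. All values below are assumptions: p = 75%, q = 30%. The last column is the exact binomial probability of at least 175 passes among 250, since 175/250 = 70%.

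| f | Of 250 | Observed rate | P(at least 175) |
|---|---|---|---|
| 0% | 0 | 75.0% | 96.9% |
| 2% | 5 | 0.98 × 75 + 0.02 × 30 = 74.1% | 93.8% |
| 5% | 12.5 | 0.95 × 75 + 0.05 × 30 = 72.75% | 85.2% |
| 10% | 25 | 0.90 × 75 + 0.10 × 30 = 70.5% | 59.9% |
| 20% | 50 | 0.80 × 75 + 0.20 × 30 = 66.0% | 10.1% |

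The share that would bring a true 75% down to 70% is (75 − 70)/(75 − q):

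- q = 0: 6.7%, about 17 of 250
- q = 30%: 11.1%, about 28 of 250
- q = 40%: 14.3%, about 36 of 250
- q = 50%: 20%, or 50 of 250

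**Step 5. Direction.** If former trial participants were better informed than routine users, the shift would reverse. With q = 90% (assumed) and f = 2%, the observed rate is 0.98 × 75 + 0.02 × 90 = 75.3%.

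**The case against.** The strongest reply is that the sampling frame does most of the work. Posters hang in Canadian settings where people obtain PrEP, recruitment is limited to regions with public listing, the vendor is optional, and concurrent studies of long-acting injectable PrEP are already excluded. What remains is a narrow group, and nothing in the protocol shows that anyone in the frame belongs to it. All of this stands. It makes such respondents few, but it does not make them ineligible. A reader might infer that the survey admits anyone who has ever had an injection; the recruitment rules and the exclusion criterion do not support that.

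A second reply concerns exposure to the aRMMs. A reader might infer that anyone who never received an aRMM should be kept out of the denominator. The protocol does not support that either. Whether users have used the aRMMs is primary objective 1, so a Canadian user who never saw the User Guide belongs in the survey, and that non-use is a valid result. The gap concerns only people whom the Canadian program was never meant to reach. Likewise, a person first injected abroad or in a trial who then has injections in Canadian routine care belongs in the population.

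Finally, the screener and the survey instruments (Annex 2) are not reproduced in the available text, so whether they ask about place or setting of injection cannot be checked. If they do, such respondents could be identified at analysis, but the stated criterion would still admit them.

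**Conclusion.** The mismatch is real and minor. The user criterion and the user exposure definition are wider than the population named in the primary aim and wider than the matching HCP criteria.

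The size of the effect cannot be derived from the documents, and neither can its direction. With the assumed pass rates of 75% and 30%, a 2% share costs 0.9 points, against a half-width of 5.7 points at 70% and n = 250. Under those same assumptions the share would have to exceed about 11% before a true 75% fell below the cut-off, and recruitment through Canadian PrEP settings makes a share of that size unlikely.

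A reader might infer that even a very small share would turn success into failure. That follows only if the true pass rate is placed exactly at 70% and the added respondents are assumed to do worse. The documents give no basis for either assumption.

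The case for acting rests on matching the criterion to the stated target population, and on the difficulty of recovering the source of injection later if it was never asked. It does not rest on a demonstrated effect on the primary result.

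**What to change.** In Section 7.2.2 (User KAB Survey) and in the user survey exposure definition in Section 7.3.1, use one wording: *at least one injection of CAB-LA for HIV PrEP received in Canada, outside a clinical trial*. Add one matching question to the screener.

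A launch-date clause is largely redundant. Section 7.1 gives 15 July 2024 as the date of commercial availability, so an injection in Canada outside a trial will nearly always fall on or after it.

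Do not make receipt or use of an aRMM an entry condition. Canadian users who never saw one should stay in the denominator.

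The cost is one criterion, the matching definition and one screener item. A few respondents may be screened out. If recruitment still reaches 250, the planned precision of ±6.2 points is unchanged. If the condition were instead applied only at analysis, using an added question, and 5% or 10% of respondents were removed (leaving 238 or 225), the half-width at 50% would be 6.35 or 6.53 points.

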### *Apretude Supports Program Database Analysis*

To be eligible for inclusion in the study, individuals within the Apretude Supports Program database must meet all of the following criteria:

- Evidence of a personally signed and dated informed consent document (i.e., Apretude Supports Program patient enrolment form) consenting to program analysis; and
- Have received at least one injection of CAB-LA (with or without the optional lead-in treatment), with the first injection taking place between July 2024 and October 2026.

### **7.2.3. Exclusion Criteria**

#### *HCP KAB Survey*

HCPs meeting any of the following criteria will be excluded from the study:

- Physicians, nurses or pharmacists in training.

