## Setting

For the survey component of the study, the setting will be web-based (online). For the retrospective analysis, the study setting will include various Apretude Supports Program sites across Canada: As of April 21, 2025, there are 159 sites across Canada, with sites distributed between Ontario (78), Quebec (40), British Columbia (15), Alberta (9), New Brunswick and Saskatchewan (5 each), Manitoba and Nova Scotia (2 each), and one site each in Newfoundland and Labrador, Prince Edward Island, and the Northern Territories. The Apretude Supports Program is designed to facilitate access and provide assistance to qualifying individuals who have been prescribed CAB-LA. The services under the program may include reimbursement investigation and/or financial assistance, assistance with drug administration, medication dispensing, medication delivery or testing, and disease and medication resources. This Program is a ViiV initiative and is administered by third-party service providers, specifically Bayshore Speciality Rx Ltd, selected by ViiV.

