**Table 7. Survey questions categorization by risk message category**

Risk Message Topic	User Survey		HCP Survey		
	Knowledge	Behaviour	Knowledge	Attitude	Behaviour
Comprehensive prevention strategy	Q31, Q32, Q38	Q47, Q48, Q49	Q13		Q30, Q33
Risk of developing drug resistance	Q36, Q37, Q39, Q40	Q51	Q15, Q16, Q17, Q23, Q24		Q32, Q39, Q40
Adherence	Q33, Q35, Q41, Q44, Q45	Q46	Q18, Q19, Q20, Q21, Q22	Q25	Q26, Q29, Q34
Regular monitoring/ HIV-1 seroconversion	Q34		Q14		Q27, Q28, Q31, Q35, Q36, Q37, Q38

**Abbreviations:** HCP, Healthcare provider; HIV, Human immunodeficiency virus; Q, question.

*Assessment of success*

For the HCP and CAB-LA user surveys, the proportion of correct or appropriate responses to the access, knowledge, attitude (for HCP), and behaviour questions related to the primary objective will be summarized, across questions, categories (access, knowledge, attitude, behaviours) and participants.

For this study, a success threshold (i.e., optimal knowledge, attitude, and behaviour) of 80%, which is commonly used by convention, will be adopted at the individual level. In other words, an individual will be deemed to have met the success threshold if they answer  $\geq 80\%$  of questions within each KAB domain correctly or appropriately. Therefore, there will be a separate score for knowledge and behaviour. At the population level, we propose a success cut-off of 70% defined as at least 70% of HCPs and CAB-LA users meeting the success threshold (i.e., answer  $\geq 80\%$  of questions within the KAB domain correctly or appropriately) at the time of assessment.

While some published KAB studies have conducted surveys at two time points, we will be conducting a one-time assessment because we anticipate that 70% of HCPs and CAB-LA PrEP users surveyed would likely achieve the success threshold.

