## 7.10. Other Aspects

In the event that KAB success thresholds are not reached, it will be important to identify possible reasons for failure and areas for potential intervention and improvement. By design, the survey will include questions that are not used in the scoring of KAB, but used to understand general use of aRMMs and potential reasons for suboptimal use. Free-text

#{vault:document\_date\_\_v}

Protocol for Non-Interventional Studies PASS Studies and Non-PASS Studies (4.0) March 2024

Template Doc ID: TMF-15706807

Parent Doc ID: VQD-SOP-066694

response options will be available in key questions in order to capture rich information that may inform strategies to improve the uptake of the optimal behaviours detailed in the aRMMs.

Since Apretude's approval in Canada in May 2024, the GSK/ViiV medical team has proactively developed programs for HCP education which can be leveraged if appropriate. These programs are based on a national learning needs assessment for HIV prevention and include other faculty-driven learning activities that provide key information on PrEP in general, but also on new modalities like Apretude. The educational focus is on acquiring knowledge (in-depth data review), but also on attitude and skills (data-light with focus on experience sharing and practical tips & tricks) to support HCPs in the safe use of Apretude. Another tool recently made available to HCPs is the Apretude Prevention Guide, which was developed by a group of experts across Canada, including infectious diseases specialists, family physicians, nurse practitioners and pharmacists specializing in HIV and PrEP. Of note, the details of the aRMMs as well as its resource page is provided to HCPs in this guide.

Based on the survey methodology, we expect that we will be able to identify whether the low level of success follows specific trends. For example, suboptimal behaviour in managing users who discontinue the regimen may be associated with a specific type of HCP, low levels of knowledge about adherence among users may be linked to specific regions, or systematic demographic differences may exist between participating groups, such as those with missing data compared to those who completed the survey. If so, we will focus our efforts on leveraging the existing education resources and adapting/tailoring them to appropriately addressing these gaps identified from this study.

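### HCPs linked to the sponsor, the study team, the support-programme vendor or the CAB-LA materials can count in the 70% HCP verdict, and no visible provision identifies them

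*Protocol*

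**What the plan says.** Protocol section 7.2.3 gives one HCP exclusion: "Physicians, nurses or pharmacists in training". Section 7.2.2 requires the respondent to be a physician, nurse or pharmacist able to complete the survey in English or French, and to meet one of three experience criteria outside a clinical trial. The widest of these is "Have been or are currently involved in some aspect of CAB-LA management for HIV PrEP in Canada". Under Logistics and Monitoring (7.5.2), entry is through a "brief screening questionnaire to assess eligibility for survey participation against study inclusion criteria".

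On the support programme, the Setting text in 7.2 states "This Program is a ViiV initiative and is administered by third-party service providers", chosen by the sponsor. Its services may include "assistance with drug administration, medication dispensing, medication delivery or testing".

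Section 7.10 describes faculty-driven education programmes developed by the sponsor's medical team. It also describes an Apretude Prevention Guide that gives HCPs the details of the aRMMs and was "developed by a group of experts across Canada, including infectious diseases specialists, family physicians, nurse practitioners and pharmacists specializing in HIV and PrEP".

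The success rule, under Assessment of success in 7.3.2, is a point-estimate rule: an individual succeeds with at least 80% of a domain's questions answered correctly or appropriately, and the population cut-off is "at least 70% of HCPs and CAB-LA users meeting the success threshold".

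**The concern.** The primary aim is to tell Health Canada whether the aRMMs are effective among HCPs. People who wrote the materials, teach from them, work for the sponsor or are contracted to deliver its programme may know the risk messages for reasons other than the aRMMs having reached them in ordinary practice. As written, each such person counts as one of about 100 respondents, and each is more likely to raise the pass share than to lower it. A confidence interval does not cover that kind of error.

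The consequence is also lopsided. The assessment is planned once. Section 7.10 ties its search for causes and corrective action to thresholds not being reached, and offers a 3-year re-assessment only if needed. A result pushed just over 70% would remove the trigger for both. If affiliation is not asked at screening, it will be hard to reconstruct after recruitment closes, whatever the SAP says.

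**Working it through.** **Is there a provision that removes or flags these HCPs?** Going through the places where one could sit:

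- Exclusion (7.2.3): trainees only.
- Screening (7.5.2): described as a check against the inclusion criteria.
- Integrity checks (7.5.2): aimed at repeat completion, suspicious e-mail addresses, near-identical records and unrealistic completion times.
- Collected characteristics (Table 2): the nearest item is receipt of CAB-LA information through a company representative. It would flag many ordinary HCPs and does not record employment, authorship or a study role.
- Sensitivity analysis (7.7): removes poor-quality responses only.
- Limitations (7.9): name voluntary participation and possible non-representativeness; the visible text does not mention affiliation.

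**The plan's own precision.** Table 13 uses half-width = 1.96 × √(p(1−p)/n). For n=100:

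- p=0.50: 1.96 × √(0.25/100) = 9.8 points, as stated.
- p=0.70: 1.96 × √(0.21/100) = 9.0 points, as stated.

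**Effect on the verdict.** From the protocol: n=100, and success means 70 or more respondents passing. Assumed, because the protocol gives no figures: k linked respondents pass with probability q, and 100−k independent respondents pass with probability p.

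Expected share = [k·q + (100−k)·p]/100. With p=0.65, q=0.95 and k=10, this is (9.5 + 58.5)/100 = 68.0%.

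P(success) = Σₓ P(Bin(k,q)=x) × P(Bin(100−k,p) ≥ 70−x), computed exactly. With q=0.95:

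| Linked, k | Expected share, p=65% | P(success), p=65% | P(success), p=60% |
|---|---|---|---|
| 0 | 65.0% | 0.173 | 0.025 |
| 2 | 65.6% | 0.206 | 0.034 |
| 5 | 66.5% | 0.263 | 0.052 |
| 10 | 68.0% | 0.376 | 0.100 |
| 20 | 71.0% | 0.638 | 0.291 |

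Varying the assumed pass rate of linked HCPs at p=65%:

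- q=0.90: 0.200 (k=2), 0.246 (k=5), 0.336 (k=10).
- q=1.00: 0.212 (k=2), 0.280 (k=5), 0.417 (k=10).

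The pattern does not depend on the exact value of q. Each linked respondent moves the expected share by (q−p) points, which is 0.30 at q=95% and p=65%. Ten of them move it by 3.0 points, well inside the 9.0-point half-width at 70%, but as a systematic shift in one direction.

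**Which scores are affected.** The 80%/70% rule is framed as knowledge, attitude and behaviour; access to the aRMMs is reported separately. Table 5 marks most HCP behaviour topics and the attitude item as for prescribers only. For linked respondents who do not prescribe, the effect is therefore mainly on knowledge.

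**The case against.** The strongest reply is that the size rests on invented inputs. The protocol does not say how many linked HCPs exist, how many would respond, or how they would score. This stands, and it is why the table starts at low counts: with one or two linked respondents the effect is slight.

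Second, the facts can be over-read. A reader might infer that the vendor employs nurses and pharmacists who inject CAB-LA. The protocol says only that services may include assistance with administration, so clinical staffing is an inference. A reader might also take the guide's authors to be sponsor staff; the protocol calls them experts across Canada. One contributing author has a hospital affiliation, but no clinical role is stated. These points stand.

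Third, not everything can be seen. The survey instruments are not shown, and parts of 7.7.2 and 7.9 are redacted. The claim can only be that no visible provision identifies these HCPs.

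Fourth, excluding vendor clinicians outright could do harm. Section 5.2 directs the aRMMs at HCPs prescribing and administering CAB-LA, so vendor staff who do administer it belong to the target population. This stands and limits the fix.

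Fifth, a one-time survey without a comparator cannot separate the aRMMs from sponsor education for any respondent. This is true, and flagging linked HCPs does not cure it. It does keep the most evident cases from deciding the verdict unseen.

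**Conclusion.** The gap is real. Read as written, the eligibility text lets HCPs with a direct link to the sponsor, the study team, the vendor or the CAB-LA materials count in the 70% verdict, and nothing visible in the protocol removes or flags them.

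What follows is a risk of upward bias, mainly in knowledge, and not a demonstrated one. Under assumed pass rates of 65% and 95%, the chance of a success verdict goes from 17% with no linked respondents to 21% with 2, 26% with 5 and 38% with 10. The issue matters only if at least a handful take part and the true rate lies near the cut-off.

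Two stronger readings are not supported. One is that the verdict will be inflated: the number of linked respondents is unknown and may be nil. The other is that access, knowledge and behaviour would all be inflated: access is outside the 80%/70% rule, and most behaviour items go to prescribers only.

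It is worth settling before recruitment opens, because affiliation has to be asked at entry.

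**What to change.** 1. In 7.2.3 (HCP KAB Survey), exclude current employees of the sponsor and members of the study team.
2. Add one screener question covering current employment by or contract with the support-programme vendor, having helped develop the aRMMs or the Apretude Prevention Guide, and having served as faculty in the sponsor's CAB-LA education.
3. Keep HCPs who answer yes in the survey, and report the 70% verdict with and without them as a prespecified sensitivity analysis, giving their number.

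The cost is one exclusion line, one screener question and one extra table row, with a slightly smaller eligible pool. If nobody answers yes, the row shows that and strengthens the result.
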